Knowing that the interdental space is surrounded by avascular root surfaces on either side, the feeding source of blood supply comes from the gingivo-papillary unit and the crest of the alveolar bone. Any tear or excess trauma to this narrow band of papillary tissue results in compromised vascularity which leads to necrosis. This gives attention for the urgency of

maintaining papillary integrity during all dental procedures and lessening traumatization to consider preventing its loss (*Zucchelli 2008*).

Several attempts for augmentation and rebuilding techniques aiming at reconstructing the defective papilla encountered major limiting factor pointing at the minor blood supply feeding the small fragile interdental papilla (*Georgieva*, etal. 2017; Alahmari 2018; Thomas etal. 2000).

The injection of hyaluronic acid gel have been considered of the latest conventional non invasive techniques for treatment of deficient papilla to escape drawbacks of surgeries however still entails unpredicted complete gingival papilla improvement owing to the relative compact nature of the gingiva which is influenced by the gingival biotype that could hinder the positive outcomes on favor of thick biotype that could help to enrich the effect of hyaluronic acid thru accelerating the thick connective tissue related abundance of gingival fibroblast proliferation, promoting the generation of collagen fibers (*Becker etal. 2010*).

Karring etal 1974 tested papillary tissue augmentation through influencing connective tissue cell proliferation, providing clot stability, protecting the reconstructed site during wound healing. He reported that sub-epithelial connective tissue possess the genetically determined factor to induce changes in the differentiation of the nature of the epithelium developing at a region. Sub-epithelial connective tissue graft has been successfully used for the double blood supply it provides, closer color blend of graft to the adjacent tissue and absence of keloid healing.

However, because of the low blood supply and the anatomic restriction of the recipient gingival papilla, the result is unpredictable unless successful surgical attempt aiming for clot stability influenced by the defect related flap design, to avoid early wound failure and exposure of the treated area occurred (*Langer etal. 1985; Han & Takei 2000*).

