Many surgical approaches using traditional periodontal plastic and augmentation procedures have been proposed to overcome the problem of the low blood supply. However, Due to the number and location of incisions, which can disrupt the blood supply, techniques with new flap designs were found to be invasive with limited success and long-term stability needed for complete healing (*Carranza & Zogbi 2011; Singh etal 2013*).

A new surgical technique called Tube technique has been developed for protection of the

wound without disturbing the blood supply of the graft by precise flap design allowing containment of the graft within a rich vascular enclosed bed, thereby predictably offering reliable and satisfactory results (*Hooshang et al 2020*).

Our randomized clinical trial target is comparing between the clinical efficacy of surgical Tube technique and Hyaluronic Acid gel injection in reconstruction of the interproximal papilla in patients with class II papillary defect.

Statement of the problem:

Restoring defective interdental papilla partially or totally in structure and function creates a challenge in dental field owing to the small working space and limited blood supply to the area. This led to the innovation of different techniques for treatment of defective interdental papilla that aimed at papillary tissue augmentation reported to be attained through influencing connective tissue cell proliferation, providing clot stability, protecting the reconstructed site during wound healing (Nordland, 2018; Singh etal. 2013)

Among these techniques is the injection of hyaluronic acid gel have been considered of the latest non-invasive technique to escape drawbacks of surgeries. Though proved to have some positive results in the literature however still entails unpredicted complete gingival papilla improvement because of the diverse injection methods, cycles, dosage, and the course of treatment that needs further optimization, in addition to the lack of unified patient inclusion criteria, especially the gingival biotype (*Langer etal. 1985;Han & Takei 2000*).

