It is a minimally invasive non-surgical injection of hyaluronic acid that observed to overcome the major limiting factor in most surgical techniques regarding the limited blood supply and the small working space. Supported by a recent study conducted by *Jinng etal.* 2019, who reported significant increase in the height of the gingival papilla and reduction of the area of the black triangle between baseline and 3 or 6 months in a group with thick gingival biotype after injection with hyaluronic acid, that was adding possible maximum effect with minimal postoperative hazards.

II.B. Objectives of the study:

7. Aim of the study

The aim of this randomized clinical trial is to compare the clinical effect of surgical Tube technique versus Hyaluronic Acid gel injection in reconstruction of the interproximal papilla in patients with class II papillary defect.

Picots:

P: Population: patients with class II papillary defect.

I: Intervention: Tube technique hosting sub-epithelial connective tissue graft.

C: Control: Hyaluronic acid injection.

Primary outcome: interdental papilla loss (Decrease of black triangle) (mm2)

Secondary outcome: assessment of gain in papillary height, radiographic distance between (CP-

BC), assessment of CAL. PD reduction, amount of gingival recession.

T: Time frame: 6 months.

S: Study design: Randomized clinical trial.

Hypothesis:

Null hypothesis: There is no difference in the gain in papillary height comparing hyaluronic acid injection versus Tube technique in patients with class II papillary defect.

8.Trial design

The study is designed as a superiority, 2 arm parallel groups, randomized clinical trial with allocation ratio 1:1.

III. Methods

A) Participants, interventions and outcomes

9. Study settings:

This study will be carried out on patients enrolled from the outpatient and postgraduate clinics of Oral Medicine and Periodontology department, Faculty of Dentistry, Cairo University.

10. Eligibility criteria:

Inclusion Criteria:

- Highly motivated patients with papillary deficiency types II, according to *Nordland* and *Tarnow 1998* classification will be selected, having at least one deficient papilla in the anterior region.
- Distance between the contact point and inter-proximal bone crest (CP-BC) of ≤ 7 mm and probing depth of ≤ 4 mm at the deficient papillary site (*Abdelraouf etal. 2019*).
 - Patients with full mouth plaque index (PI) and gingival index (GI) scores should be between 0-1.

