This power analysis used interdental papilla loss after six months as the primary outcome. Based upon the results of Awartani FA and Tatakis DN (2016), the mean and standard deviation (SD) for control group were 0.71 (0.74) mm2. The minimal clinically significant difference was 1 mm2according to expert opinion. Using alpha (α) level of (5%), β level of 0.8 (Power = 80%); the effect size for independent samples t-test (d) was 1.32 and the minimum estimated sample size was 10 sites per group. Sample size was increased to 12 sites per group to compensate for a drop-out rate of 20% after six months. Sample size calculation was performed using PS Power and Sample Size Calculations Version 3.

15. Recruitment strategy

- The main investigator will be responsible for recruitment of patients.
- Patients will be selected from the outpatient clinic of the Oral Medicine and Periodontology
 Department, Faculty of Dentistry Cairo University.
- Screening of patients will continue until the target sample is achieved.
- Identifying and recruiting potential subjects will be achieved through patient database.
- 1. One year.
- 2. Candidate self-funding

B) Assignment of interventions

16. Allocation

16a. Randomization

The patients will be randomly allocated to either the intervention group or the control group using computer generated random numbers that will be performed by the supervisor. The patients will be allocated in a ratio of 1:1.

16b. Allocation concealment mechanism

The two groups will be equally prepared for both surgical procedures. Then the decision of which group will receive Hyaluronic acid injection and which will Tube Technique will be taken according to the randomized numbers placed in opaque sealed envelopes. The number will be picked by the supervisor.

16c. Implementation

The supervisor will be responsible for generation of allocation sequence as will as assign the patients to the 2 intervention groups. The main investigator will be responsible for patient enrollment.

17. Masking/blinding:

Due to the type of intervention only the outcome assessor and the statistician will be blinded. Single blinded:

- Blinding of the participants is not applicable.
- Blinding of the operator is not applicable.
- Outcome assessor (primary and secondary outcomes) and biostatistician will be blinded.

Key elements of Random Sequence Generation in protocol are:

- 1-Method of random sequence generation (computerized random number generator).

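### Gingival biotype is named as an important influence on the hyaluronic acid response, but the protocol does not restrict, record or balance it

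*Protocol*

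**What the plan says.** **Background.** The text under section 6 describes the gingiva's compact nature as something "which is influenced by the gingival biotype that could hinder the positive outcomes on favor of thick biotype"; the Review of literature repeats this. The Statement of the problem attributes unpredictable results with hyaluronic acid to two things. One is variation in treatment, "because of the diverse injection methods, cycles, dosage, and the course of treatment that needs further optimization". The other is patient selection, "in addition to the lack of unified patient inclusion criteria, especially the gingival biotype". Item 4 of the rationale and the Comparator paragraph both support hyaluronic acid with improvement seen "between baseline and 3 or 6 months in a group with thick gingival biotype after injection with hyaluronic acid".

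**Methods.**
- Section 10 selects class II patients "having at least one deficient papilla in the anterior region", with "Distance between the contact point and inter-proximal bone crest (CP-BC) of ≤ 7 mm and probing depth of ≤ 4 mm", low plaque and gingival scores and good health. No inclusion or exclusion criterion concerns biotype or gingival thickness.
- The baseline chart in section 11a lists papilla class, CP-BC, plaque and bleeding indices, probing depth, attachment level and recession.
- The outcome table and definitions (section 12) and the timeline (section 13) contain no biotype measurement.
- Section 16a reads: "The patients will be randomly allocated to either the intervention group or the control group using computer generated random numbers", in a 1:1 ratio. It names no stratification factor. The list of key elements at the end of section 17 leaves the type of randomisation open between simple, blocked and stratified.

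**The concern.** The background treats biotype as a patient characteristic that helps to explain how well the comparator works. The methods fix the product, the number and timing of injections and the needle position, so they address part of the variation blamed for earlier results. The patient characteristic singled out in the same sentence is left open.

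Two things are at stake. First, in a trial this small the arms can differ by chance in their share of thick-biotype patients. If biotype affects the outcome, that difference adds error which a recorded baseline variable could remove. Second, if hyaluronic acid does poorly, the protocol's own background suggests an explanation (mostly thin tissue in that arm) that nobody could check. Eligibility, baseline data and allocation are protocol matters, so a separate statistical analysis plan could not make good an uncollected variable.

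**Working it through.** **1. The plan's own sample size.** Inputs from section 14: SD 0.74 mm2, difference 1 mm2, alpha 5% (two-sided assumed), power 80%. The effect size is 1/0.74 = 1.35; the protocol states 1.32. The two-sample t-test needs 9.66 per group, so 10, as stated. The stated 12 is 10 x 1.2. The point about biotype does not depend on these figures, but they set the scale.

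**2. Standard error of the difference at 12 per arm.** 0.74 x sqrt(2/12) = 0.74 x 0.408 = 0.302 mm2.

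**3. Chance of an uneven split.** The documents give no biotype prevalence. Assume 24 patients, exactly 12 of them thick, 12 per arm (hypergeometric):
- P(6 v 6) = C(12,6)^2 / C(24,12) = 853,776 / 2,704,156 = 0.316
- P(7 v 5, either way) = 2 x 792^2 / 2,704,156 = 0.464
- P(8 v 4 or worse) = 1 - 0.316 - 0.464 = 0.220

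**4. Shift caused by an 8 v 4 split.** Let D be the difference in black-triangle outcome between thick and thin, assumed equal in both arms. The shift is (8/12 - 4/12) x D = 0.33 x D. The documents give no value for D, so take 0.5 to 1 mm2 as an assumption:
- D = 0.5: 0.17 mm2, and 0.167/0.302 = 0.55 SE
- D = 1: 0.33 mm2, and 0.333/0.302 = 1.10 SE

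Against the 1 mm2 target difference this is 17% to 33%.

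**5. How far the assumptions matter.**
- *Number of thick patients left to chance.* With a true prevalence of 30% to 70% and independent binomial arms of 12, a gap of at least 4/12 has probability 12% to 15%, and a gap of at least 3/12 has 26% to 31%. The 22% above is therefore specific to an exact half-and-half sample.
- *Biotype acting only under hyaluronic acid.* An 8 v 4 split then moves only that arm's mean, by (6/12 - 4/12) x D = 0.17 x D, or 0.08 to 0.17 mm2.
- *Section 11's 18 sites per group instead of 12, one site per patient.* With 18 of 36 thick, the same one-third gap (12 v 6 or worse) has probability 1 - (48,620^2 + 2 x 43,758^2 + 2 x 31,824^2) / 9,075,135,300 = 0.094, against 0.220 at 12 per arm.
- *Plausibility of D.* In an even mix, biotype contributes variance D^2/4. Against a total of 0.74^2 = 0.548, that is 0.0625/0.548 = 11% for D = 0.5 and 0.25/0.548 = 46% for D = 1. The upper end is demanding.

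**6. What a covariate could recover.** If 0.74 is the total SD and D is equal in both arms, removing 11% to 46% of the variance takes the SE from 0.302 to between 0.302 x sqrt(0.886) = 0.284 and 0.302 x sqrt(0.543) = 0.223 mm2, before the loss of one degree of freedom.

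**The case against.** The best defence is that randomisation already protects the comparison. A chance difference in biotype mix is random error, which the standard error and the significance level allow for. Enrolling all biotypes is a legitimate choice, and the stated aim is tube technique against injection in class II defects, not the role of biotype. This stands. The most likely uneven split at 12 per arm, 7 v 5, is also the smallest possible under the assumptions above and moves the difference by only 0.17 x D.

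Some stronger readings are tempting but lack support:
- *Biotype decides the response.* The text says it influences the response and could hinder it, and names injection method, cycles, dosage, course and other factors too.
- *The trial repeats the defect it set out to correct.* No objective undertakes to resolve variation by biotype.
- *The tube arm is equally affected.* The Review of literature says only that the technique is sensitive when recipient tissue is delicate; it does not mention biotype there.
- *The gap cannot be repaired because the graft thickens the tissue.* That could apply only to the tube arm, and the one thickening figure (0.75 to 2 mm) comes from a different flap technique.

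Covariates are also commonly left to the statistical analysis plan, which is not shown. That covers the choice of model, but not the failure to plan collection of the variable.

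**Conclusion.** The point holds as a modest, inexpensive improvement. The protocol gives biotype real weight in its background and no place in its methods. The consequence is avoidable imprecision and a result that cannot be interpreted by biotype. A reader might infer that the treatment comparison is biased or invalid; the documents do not support that, because allocation is random.

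The illustrative size is a 22% chance of a split that shifts the difference by 0.17 to 0.33 mm2, about 0.6 to 1.1 standard errors. It rests on 12 patients per arm, exactly half thick, and D of 0.5 to 1 mm2 acting equally in both arms. None of the last three comes from the documents. The figure falls if the number of thick patients varies by chance, if biotype matters only under hyaluronic acid, or if 18 per group is the true number. Sections 11 and 14 disagree on that number, which is a separate matter to reconcile.

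**What to change.** Add gingival biotype (thick or thin, by one defined method, at the study site) to the baseline chart in section 11a, recorded before allocation. Prespecify it as a single covariate in the between-group comparison of black-triangle area, and report the biotype mix by arm. If a patient contributes more than one papilla, record it for each site.

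Stratified allocation is optional and not required: in a trial this small it brings sparse strata, and a patient with sites of both types would fit neither stratum. Estimates within biotype would rest on about six patients per cell under an even mix, so they should carry no inferential weight.

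The cost is a brief extra baseline assessment and one degree of freedom. Treatment, eligibility and sample size do not change.

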 - Healthy patients free of any medical condition.

Exclusion criteria:

- Patients with medical conditions that may affect periodontal healing or regeneration.
- Patients with a history of allergic reactions, pregnant or breastfeeding females,
 smokers and alcoholics
- Patients with current or previous drugs intake that may predispose to gingival enlargement.
- Patients under orthodontic treatment or had orthodontic treatment in the past six months.
- Carious teeth, proximal restorations or fixed prosthesis.
- Patients with a history of traumatic oral hygiene measures or periodontal surgeries over the last six months at the area of interest or having any scar tissue.
- Poor oral hygiene patients.

11. Interventions

11a-General operative procedure

- The patients who fulfil the inclusion criteria will be enrolled.
- The nature of the study will be explained to each patient as well as the importance of compliance with pre- and post-operative instructions and follow-up visits.
- Each patient will be asked to sign an informed consent (appendix 1)
- After enrolment, periodontal examination and full periodontal charts will be recorded for each patient including Papilla Class I1, CP-BC plaque Index (*Leary et al., 1967*), gingival bleeding Index (*Ainamo & Bay, 1975*), probing depth (PD), clinical attachment level (CAL) and gingival recession.

Radiographic Evaluation

Standardized digital periapical radiographs will be obtained preoperatively and at follow-up using the long cone paralleling technique. All radiographs will be obtained using the same equipment, film exposure and development conditions.

Pre-surgical therapy

- All patient will receive strict oral hygiene instructions full mouth supra and sub-gingival debridement using hand instruments and ultrasonic scalers under local anesthesia.
- Four to six weeks following pre-surgical therapy, a periodontal re-evaluation will be performed to confirm the suitability of the chosen sites for this periodontal surgical study.
- The clinical and radiographic parameters will be recorded at baseline

The patients will be randomly assigned into two groups: A total of 36 sites (18 site per group)

Group A (Intervention): Patients will receive Tube technique.

Group B (Control): Patients will receive Hyaluronic acid.

Surgical Procedures

Group A (Intervention): Patients will receive Tube technique (Hooshang et al. 2020).

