- 2- Allocation ratio (1:1, 2:1).
- 3- Type of randomization: simple, blocked, stratified.

c) Data collection, management, and analysis:

18. Data collection methods

- All the data of the patients included in the study will be recorded from them or extracted from the patient's periodontal chart.

- Telephone numbers of all patients included in the study will be recorded as a part of the written consent.
- All patients will receive a phone call at the time of the pre-determined follow up dates.

19. Data management:

Excel sheet program will be used though a computer system to manage the data with a secured password.

20. Statistical methods:

- The outcome used (State 1ry or 2ry): interdental papilla loss area (mm2)
- Values used for outcome (e.g. mean difference, percentage, proportion..... etc): mean and standard deviation
- Entry 1: (mean difference between 2 groups, mean and standard deviation of group 1, proportion 1 or estimated prevalence):

Minimal clinically significant difference = 1 mm2 according to expert opinion

• Entry 2: (standard deviation of control group, mean and standard deviation of group 2, proportion 2 or clinically important difference):

Mean of the control group = 0.71

SD of control group = 0.74

- Alpha level of significance: 0.05
- Effect size used in calculation: d = 1.32
- Power of the study: 0.8
- Statistical test used: Independent samples t-test
- The calculated sample size: 10 sites per group.
- Increased number for anticipated missing data: Sample size will be increased to 12 sites per group to compensate for a drop-out rate of 20% after six months.

D) Data monitoring:

21. Monitoring

No formal data monitoring committee will be needed since it is a study with known minimal risks.

22. Harms

Postoperative pain and/or swelling will be managed through analgesics.

23. Audit

Auditing of the study design will be done by the evidence-based committee – Faculty

Dentistry – Cairo University.

IV. Ethics and dissemination

24. Research ethics approval

This protocol and the template informed consent form will be reviewed by the Ethics Committee of Scientific Research -Faculty of Dentistry- Cairo University.

25. Protocol amendments

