Any modifications to the protocol which may have an impact on the conduct of the study, potential benefit of the patient or may affect patient safety, including changes of study objectives, study design, sample sizes, study procedures, or significant administrative aspects will require a formal amendment to the protocol. Such amendment will be agreed upon by the Council of Oral Medicine and Periodontology Department and the Faculty of Dentistry, Cairo University.

26. Informed consent

Researcher will introduce the trial to patients and provide full explanation of its aim and benefits in layman language. Patients will then be able to have an informed discussion with the researcher. Researcher will obtain written consent from patients willing to participate in the trial. All consent forms will be translated into Arabic.

27. Confidentiality

All study-related information will be stored securely. All participant information will be stored in locked file cabinets in areas with limited access. All reports, data collection, process, and administrative forms will be identified by a coded ID [identification] number only to maintain participant confidentiality. All records that contain names or other personal identifiers will be stored separately from study records identified by code number. All local databases will be secured with password-protected access systems.

28. Declaration of interest

If there will be any conflict of interest it will be declared.

29. Access to data

The principal investigator and the supervisors will have access to the data sets. All data sets will be password protected. To ensure confidentiality, data dispersed to project team members will be blinded of any identifying participant information.

30. Post-trial care

All patients will be followed up for six months after the clinical trial is over.

31. Dissemination policy

- Study results will be published as partial fulfillment of the requirements for Doctorate's degree in Periodontology. - Topics suggested for presentation or publication will be circulated by the authors.

32. Informed consent

VI. Statement of originality

To the best of our knowledge, no randomized clinical trial has been published that involve comparing the clinical effect of surgical tube technique to hyaluronic acid gel injection in reconstruction of the tnterproximal papilla in patients with class II papillary defect.

VII. References

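### Section 11a assigns 18 sites per group, Sections 14 and 20 give 12, and no stated input leads to 18

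*Protocol*

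**What the plan says.** Section 11a (general operative procedure) states: "The patients will be randomly assigned into two groups: A total of 36 sites (18 site per group"). The total and the per-group figure agree with each other, since 2 × 18 = 36.

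Section 14 (sample size) states that "the minimum estimated sample size was 10 sites per group" and then: "Sample size was increased to 12 sites per group to compensate for a drop-out rate of 20% after six months". Section 20 (statistical methods) repeats both figures: "The calculated sample size: 10 sites per group", and "Sample size will be increased to 12 sites per group to compensate for a drop-out rate of 20% after six months". The total of 24 is not printed but follows from 2 × 12.

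Three other sections bear on the point:
- Section 15 (recruitment) makes the target the stopping rule: "Screening of patients will continue until the target sample is achieved".
- Section 25 (amendments) treats the figure as controlled: modifications "including changes of study objectives, study design, sample sizes, study procedures, or significant administrative aspects will require a formal amendment to the protocol".
- Section 10 (eligibility) admits patients "having at least one deficient papilla in the anterior region", so one patient may contribute more than one site.

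**The concern.** The number to be assigned differs from the number calculated, and the text does not explain the gap. Sections 14 and 20 agree with each other and show their inputs. Section 11a gives only the result. No allowance for clustering, a second outcome or higher power is mentioned that could carry 12 to 18.

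The consequence is practical. Recruitment that follows Sections 14 and 20 stops at 24 sites; recruitment that follows Section 11a stops at 36. Either would comply with the protocol, so the choice could be made while the trial is running, by investigators who know the treatment given. The 12 additional sites include 6 that would undergo graft surgery, and the protocol offers no reason for them. Ethics review, recruitment and the final report all need one planned number.

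**Working it through.** **Inputs** (Sections 14, 16a and 20): difference 1 mm²; control SD 0.74 mm²; stated effect size d = 1.32; alpha 0.05; power 0.80; independent-samples t-test; 1:1 allocation; drop-out 20%. The protocol does not say whether the test is one- or two-sided. I take two-sided and also show one-sided. Sites are counted as independent throughout.

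**1. Reproducing the protocol's figure.** The inputs give d = 1/0.74 = 1.351, slightly above the stated 1.32.

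Normal approximation, two-sided: n = 2(1.960 + 0.842)²/d² = 15.70/d².
- d = 1.351: 15.70/1.826 = 8.6, so 9 per group.
- d = 1.32: 15.70/1.742 = 9.01, so 10 per group.

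Noncentral t, two-sided:
- d = 1.351: 10 per group is enough (power 81.5%).
- d = 1.32: 10 per group gives 79.7%, and 11 is the first to reach 80%.

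The stated 10 is therefore reproduced, and 12 follows as 10 × 1.2.

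**2. Can 18 be reached from the stated inputs?** All rows use alpha 0.05, power 0.80 and the t-test.

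| Test | d | n per group | n/(1 − 0.2), rounded up |
|---|---|---|---|
| Two-sided | 1.351 | 10 | 13 |
| Two-sided | 1.32 | 11 | 14 |
| One-sided | 1.351 or 1.32 | 8 | 10 |

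The largest value is 14. Applying the 20% allowance a second time to 12 gives only 12/0.8 = 15.

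Going from 10 to 18 would need:
- a drop-out of 1 − 10/18 = 44% if inflation is by division;
- an allowance of 18/10 − 1 = 80% if it is by multiplication, as the protocol did it.

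Neither is 20%. Changing another input can produce 18. For example, 90% power at d = 1.32 needs 14 per group, and 14/0.8 = 17.5, so 18. But the protocol states 80% power.

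**3. Size of the discrepancy.** 36 − 24 = 12 sites, or 18 − 12 = 6 per group; 36/24 = 1.5.

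**4. Power at each candidate target.** Two-sided 5% noncentral-t power. The after-loss column averages over independent binomial 20% loss in each group.

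| Start per group | No loss, d = 1.32 / 1.351 | After 20% loss, d = 1.32 / 1.351 |
|---|---|---|
| 12 | 87.1% / 88.5% | 77.0% / 78.8% |
| 13 | 89.8% / 91.1% | 80.6% / 82.3% |
| 18 | 97.0% / 97.6% | 92.2% / 93.3% |

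**5. Drop-out allowance (minor).** 12 × 0.8 = 9.6, just under the stated minimum of 10. Dividing gives 10/0.8 = 12.5, so 13. Compared with 10 per group and no loss (79.7% and 81.5%), 12 per group after loss is lower by about 3 percentage points (2.7 on either d).

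**The case against.** The best defence is that the larger number does no statistical harm. Section 14 calls 10 a minimum, nothing forbids recruiting more, and 18 per group has ample power for the stated effect. This is correct, and it limits the harm to an ambiguous target and unexplained extra sites. It does not remove the contradiction, because Section 15 ties the end of screening to one target and the protocol supplies two.

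Other objections stand in part:
- The 44% figure depends on inflating by division. By the protocol's own multiplication it is 80%. Both are shown above, and neither matches 20%.
- The 12-versus-13 question is a small matter of convention and would not merit a finding alone.
- Thirteen per group inherits the base of 10, which falls just short of 80% at d = 1.32. Taken strictly, that d gives 11, or 14 after drop-out.
- The power figures need assumptions that the protocol does not state: a two-sided test, random loss and independent sites.
- Section 24 places ethics review in the future, so a correction made before approval may need no formal amendment.

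None of these supplies a source for 18.

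**Conclusion.** The concern holds. Section 11a plans 36 sites and Sections 14 and 20 plan 24, in the same unit, with no reconciling text. The stated inputs support 10 evaluable sites per group and 12 to 14 after drop-out on a two-sided test; they do not support 18. The difference is 12 sites, 6 per group, or half as many again as the calculated target.

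The contradiction itself rests on no assumption: it is read directly from the three sections. The power figures do rest on assumptions, namely a two-sided 5% test, random 20% loss and independent sites. Because a patient may contribute several papillae and no within-patient correlation is given, those figures hold only if sites can be treated as independent. The drop-out rounding is a side issue. The sample-size conflict must be settled before recruitment relies on either number.

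**What to change.** State one target, with its derivation, in Sections 11a, 14 and 20.

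- **If the calculated target is meant:** replace the 36 and 18 in Section 11a. Then either use 13 per group (10/0.8, 26 sites) or keep 12 per group (24 sites) and state that expected power after 20% loss is about 77% to 79%.
- **If 18 per group is meant:** give the reason in Sections 14 and 20 and state the power it delivers, about 92% to 93% after 20% loss.

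In either case, say which d is used (1.32, or 1/0.74 = 1.351), that the test is two-sided if so intended, and that the power figures assume random loss and independent sites.

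The cost is wording in three places. Relative to the 12 per group now in Sections 14 and 20, the change is 0 sites per group if 12 is kept, 1 if 13 is used and 6 if 18 is meant. If the protocol has already been approved, Section 25 may require a formal amendment.
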